#### **Participant recruitment**

Participants with ADHD and sleep problems are recruited through the ADHD clinic of the UZ Leuven (Child and adolescent psychiatry services UZ Leuven), PraxisP (the academic clinical centre of the Faculty of Psychology and Educational Sciences, KU Leuven) and the network of the advisory committee (ZitStil, VvGT, Ligant, CARs, Sig vzw, BASS). For the RCT, 92 to 100 adolescents and their parent(s)/guardian(s) will participate in the study. Only minors are recruited for the study (going to school and aged 13-17).

At the start of a diagnostic trajectory of the ADHD clinic, parent(s)/guardian(s)/guardians of the child are asked whether they could be contacted in the future for participation in clinical studies and information will be given about the current study.

Further, participants can specifically apply for the purpose of this study to the ADHD clinic. There are different possibilities to contact the researchers when participants are interested; e-mail addresses,

phone numbers and QR code (to website).

GDPR will be applied as the adolescents receive an explanation conform their development level prior to their participation in the study and the participants parent(s)/guardian(s) must always give permission to participate in the study. Adolescents are asked assent to participate in the study, and if they do not agree, they cannot participate. Even with the assent of the adolescent, consent from the parent or guardian for participation is still required. Parent(s)/guardian(s) will sign an informed consent document. In the informed consent form, permission to participate, consult the patient files and collect data are asked. Both the informed consent and assent will be discussed in detail with the participants in understandable language. Adolescents and their parent(s)/guardians(s) are told that they can follow this treatment at no cost and that they receive a reasonable compensation.

### **Ethics & procedure**

The information participants, parent(s)/guardian(s) and teachers provide may contain sensitive data and this will be taken into account at every moment during the study. Participants will be assured that all efforts will be done to protect the confidentiality: participants' names will be coded and the code will be destroyed directly after the last wave of data collection. Actual names will be matched with a code in a password protected excel file. Any identifying information such as email addresses, phone numbers, birthday,... will be kept in an excel file which will in itself be password protected. Only the researchers directly involved in performing the research will have access to this file. The data will be stored on a password protected shared network drive on the KU Leuven server. The password will only be given to the researchers. For every participant there will be multiple informants (parent(s)/guardian(s), teacher and the participant himself), but information given by another informant concerning the same participant will not be shared with the other informants.

The informed consent (parent(s)/guardian(s)/guardians) /assent (adolescent) will be send to the participants before the first meeting and they are required to sign it and send it back via email. In case of questions, the researchers are available via the phone and any uncertainties can be discussed during the first meeting. During the first meeting it is assessed whether the adolescent meets inclusion criteria for the study. In this session the K-SADS (parent(s)/guardian(s)) and the sleep interview (adolescent and parent separately) are conducted, either face-to-face or via Mynexuzhealth (or via the platform of PraxisP, backup Skype for Business). Then, the HSDQ and the subscale "Disorders in the use of substances and behavior addictions" of the MATE-Y and the SCARED are administered via Qualtrics. Next 2 subtests of the WISC/WAIS (vocabulary and matrix reasoning) are administered. Further, the adolescent is explained about the wrist actigraphy and sleep logs that need to be recorded in the next week. To remind them to fill out the sleep diary from the previous night, messages will be send when they arrive from school or other activities. Phone numbers of the participants will be stored in a separate password protected excel document on our secure network drive with only the participant number as reference. Using phone numbers exclusively requested for this study, reminders to fill out the sleep diary will be sent. In the phones, which are password protected, no names will be stored, only the participant numbers. When there is a COVID-19 outbreak, an appointment is made so that a courier service can bring the actigraphs to the adolescents. Before and after use, they will be disinfected. Another appointment will be made for one week later when either the researchers or the courier service will collect the actigraph at the home of the adolescent. The reason for not letting the adolescents send back the actigraph is that they are a very specific population. They have great problems with planning and organization. Thus, to prevent that the actigraphs are not send back or get lost, they will be picked up. Within one week after collection of the actigraph the psychologist of the study informs the adolescents and his/her parent(s)/guardian(s) whether he/she meets inclusion criteria for the study. After the screening, feedback in the form of a summary of the obtained data will be given to involved clinicians. This data will concern relevant information for the clinician giving the treatment, namely a summary of the sleep- and K-SADS interview and the results of the questionnaires (HSDQ, and MATE-Y).

When the adolescent meets inclusion criteria, the adolescent has to fill out the pretest questionnaires in Qualtrics. Parent(s)/guardian(s) of the adolescent are also asked to answer questionnaires in Qualtrics; also, they are asked to mail the link of the questionnaire (CPS) in Qualtrics to the teachers of the adolescent for their evaluation of the adolescent. Moreover the teacher will be asked how many lesson times per week he/she has contact with the participant. The names of the teachers will not be known by the researchers.

After the pretest is conducted, appointments for the treatment are made. However, participants are informed that those appointments can either happen as planned or that the treatment will take place 6 months later, due to the condition their child was assigned to. To avoid the possibility of a systematic bias in the assignment of participants to both groups (SIESTA treatment and treatment as usual (TAU) versus TAU only), randomization happens. We will use a stratified permuted block randomization based on medication use (yes/no) in blocks of 2 participants whereby an independent researcher performs the randomization. After the last treatment session, both the adolescent who followed the treatment and the paired adolescent from the TAU-group, are contacted by the researchers and provided with the actigraphs. The daily sleep logs are again filled out in Qualtrics. Within one week after the last treatment session a posttest session is planned in which the adolescent and parent(s)/guardian(s) are asked to fill out the questionnaires in Qualtrics. Filling out the questionnaires should not take longer than 1 hour for any informant. The actigraphs will again be picked up by a researcher or the courier service. The same procedure is applied during the follow-up measure after 3 months, including the actigraph/daily logs and the questionnaires. After follow-up, the treatment is provided to the adolescent in the TAU-group from that block.

In case of serious adverse events or a crisis situation, e.g. suicidality, during any phase of the study, (previously involved) clinicians will be contacted by the researchers. Also, if necessary at any time of the study, additional psychological aid can be given.

On top of the free training, adolescents receive a financial reward for participating in this study. In total 50 euros can be earned. As filling out the sleep diary is most likely to be forgotten, we reward participants for each day they fill it out. To keep participants motivated throughout the entire study this amount is divided over three time points, the pretest, posttest and follow-up.

Pre-test: 1.40 euros per day

- If they can participate, there is a maximum of 10 euros to be earned
- If they cannot participate, we give an extra 15 euros for completing the questionnaires

(maximum 25 euros)

Post test: 1.40 euros per day (they can earn a maximum of 10 euros)

Follow-up: 4.30 euros per day (they can earn a maximum of 30 euros)

The reason that we give more of the maximum amount of 50 euros during the follow-up is to motivate the young people with ADHD even more to participate in the entire study.

### **Safety**

Recording of adverse events: The participant will be asked to report any adverse event related to the study-specific intervention to the study team. These reported events will be documented by the Investigator in the source documents.

The following minimum information should be recorded for each AR:

- AE description
- start and stop date of the AR
- severity
- seriousness
- causality assessment to the study interventions
- outcome

Reporting to the Ethics Committee

The sponsor will assess whether any relevant safety information that becomes available during the study should be reported ad hoc to the EC.

The sponsor has the obligation to, once a year throughout the clinical trial (or on request), submit a progress report to the EC containing an overview of all SARs occurred during the reporting period and taking into account all new available safety information received during the reporting period.

During the first two sessions of the intervention, participants can freely report any adverse event related to the study-specific intervention to their therapist. From the third session on the following question will be posed: "Has anything happened last week that was a danger to you? Like suicidal thoughts, risk-seeking for example bingedrinking, or anything like that.". We argue that posing this question best starts during the third session as during the first two sessions the main focus is on forming a relationship and building trust. However, asking this type of question is not a risk factor to elicit suicidal thoughts or behavior even in at-risk adolescents. Research shows that talking about suicide and idealization, reduces suicide and improves mental health (e.g. Dazzi et al., 2014).

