### **Randomization and blinding**

Participants are randomly assigned to either the treatment (SIESTA+TAU) or control (TAU) group with a 1:1 allocation stratified by ADHD medication use (yes/no) and location (Leuven, Antwerp, Hasselt, Brussels, Gent, Roeselare) using permuted blocks of random sizes.[34,35] We randomize per location to ensure practical feasibility for our therapists of the KU Leuven (i.e. there is a maximum amount of adolescents that can be treated per location). Randomization is done by an

independent researcher who is not involved in the study in any way. Due to the nature of the psychological treatment neither participants nor clinicians can be blinded to allocation. Researchers who are responsible for the practical side of the study (LK, FM), are not blinded to allocation, however, the principal investigator ([name]) and the other researchers DB, BB and MD are blinded throughout the study.

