#### **Safety considerations**

Once a year throughout the clinical trial, a progress report is submitted to the Ethical Committee Research UZ/KU Leuven containing an overview of all serious adverse events (as defined by the Ethical Committee Research UZ/KU Leuven)[57] occurred during the reporting period and taking into account all new available safety information received during the reporting period. Adverse events will be recorded and systematically assessed during the sessions of the treatment. If adverse events are reported, these will be documented in a separate document by the therapists who provide the treatment and reported to the Ethical Committee Research UZ/KU Leuven, both directly after the report and annually in a summary. The following minimum information is recorded for each adverse event: 1) description, 2) start and stop, 3) severity and seriousness, 4) causality assessment to the study treatment, 5) outcome.

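### The two safety sections differ on which adverse events are collected, which serious events are listed annually, and when events go to the Ethics Committee; neither gives the control arm an active route

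*Combined protocol and SAP*

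**What the plan says.** Harms are covered in the Safety section and again, later, in the Safety considerations section under Ethics and dissemination. Both are current text, and neither is said to take precedence.

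The Safety section begins: "The participant will be asked to report any adverse event related to the study-specific intervention to the study team". It repeats that limit when it describes sessions one and two. From session three the therapist asks whether anything in the past week put the adolescent in danger, with suicidal thoughts as an example; this question is not limited to related events. On recording, it says: "The following minimum information should be recorded for each AR". The list that follows uses both AE and AR, and neither AR nor SAR is defined. The sponsor judges whether safety information should go to the Ethics Committee ad hoc. The annual report is described as "containing an overview of all SARs occurred during the reporting period" and as "taking into account all new available safety information received during the reporting period".

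The Safety considerations section speaks of adverse events without a relatedness qualifier, assessed systematically in the treatment sessions. Reported events are to be "reported to the Ethical Committee Research UZ/KU Leuven, both directly after the report and annually in a summary". The annual report is one "containing an overview of all serious adverse events", using the committee's own definition of a serious event, and the clause on new safety information appears here too.

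**The concern.** Two sets of instructions are in force for one trial, and one is narrower than the other. Which harms are logged and passed on could then depend on which section a member of staff has in hand. Someone reading a short list of events could not tell whether few occurred or few met the narrower rule.

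This matters in this population. Participants are 13 to 17 years old. Table 1 excludes depressive disorder only where there is suicide risk or active suicidality, so other depression can be enrolled. The protocol itself anticipates suicidality in the Safety, Ethics & procedure and Confidentiality sections. It describes no data monitoring committee or other independent safety reviewer, which leaves the Ethics Committee as the only independent recipient. The committee's right of access to files helps only if the event was written down.

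**Working it through.** No published figure needs reproducing and no formula applies, so the check is a comparison of the two texts.

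| Item | Safety | Safety considerations |
|---|---|---|
| Events collected | Those related to the intervention, plus answers to the danger question from session three | Adverse events in general |
| Minimum data set | For each AR | For each adverse event |
| Annual overview | SARs | All serious adverse events |
| Immediate reporting | Sponsor decides whether to report ad hoc | Sent directly once reported |
| Active questioning | In SIESTA sessions | In SIESTA sessions |

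Three cases show where the rules part.

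1. *Serious event in a SIESTA participant, judged related.* It is recorded and listed annually under both sections. Only the immediate-reporting rule differs.
2. *Serious event in a SIESTA participant, judged unrelated.* Under Safety considerations it is recorded, sent directly and listed annually. Under Safety it may surface through the danger question, which is asked in sessions three to seven (7 − 2 = 5 of the seven adolescent sessions). Even then, the recording duty is per AR and the overview covers SARs. Whether the committee hears of it depends on the sponsor's ad hoc judgement or on the new-information clause, which does not require the event to be listed.
3. *Serious event in a participant on usual treatment alone.* The Safety section asks about an intervention this person has not received, and its active question needs a session. Safety considerations also collects in treatment sessions, through the treating therapists. Neither describes an active route. With 1:1 allocation of 92, this concerns 92 / 2 = 46 planned participants.

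Could this be only an abbreviation slip? Read AR as AE and SAR as SAE throughout. The minimum data set and annual overview then agree. The relatedness limit, written out in words twice in the Safety section, remains, and so does the difference on immediate reporting.

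The number of events affected cannot be derived. The documents give neither an expected event rate nor the share likely to be judged unrelated.

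**The case against.** The best defence is that the wider rule contains the narrower one: staff who follow Safety considerations also capture every related event. That is right, so the sections are inconsistent rather than incompatible. But nothing tells staff to follow the wider one. On immediate reporting, the sponsor's discretion covers safety information at large, so it could coexist with direct reporting of individual events. That reading is possible, but the text does not state it. The danger question and the new-information clause do soften the loss. The provision in Ethics & procedure for contacting clinicians after a serious event or crisis means researchers may learn of events in either arm, but it is a care response and not a route to the committee. The committee's definition of a serious event was not available, so the exact distance between the two annual listings is open.

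Several stronger readings are tempting, and the documents do not support them.

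- *Different sites would follow different rules.* The trial is monocentre, with its own therapists travelling to several locations.
- *A suicide attempt would go unnoticed under the Safety section.* The danger question and the crisis provision could both bring it to light. What is not secured is the recording and listing.
- *Control participants can contribute no events under the Safety section, and Safety considerations cures this.* The new-information clause is not limited by arm, and Safety considerations offers no active control-arm route either.
- *The causality assessment is circular.* A participant's report and a formal rating are separate steps, and AE and AR seem to be used loosely.
- *Safety recording breaks the blind.* The Safety section says: "These reported events will be documented by the Investigator in the source documents". The principal investigator and certain researchers "are blinded throughout the study", but two researchers on the practical side are unblinded, and nothing says that a blinded person does the documenting.
- *The recorders conflict.* A therapist's separate file could itself be a source document. This needs clarifying but is not a proven contradiction.

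**Conclusion.** The point holds as an internal inconsistency that should be corrected. The sections differ on the scope of collection, on the serious events listed annually and, as written, on immediate reporting. The consequence is conditional: a serious event judged unrelated may escape the required record and annual listing if staff follow the Safety section, and its two softening provisions reduce that loss without closing it. The absence of an active control-arm route holds whichever section is followed.

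The size cannot be put in numbers beyond the 46 planned control participants. The conclusion assumes that AR and SAR carry the related-event sense which the surrounding words suggest, and that no other document in use sets a single overriding rule. It concerns the reporting of harms and does not affect the efficacy analysis.

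**What to change.** Reconcile the two sections into one rule and have each refer to it.

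- Remove the relatedness qualifier from what participants are asked to report, both in the opening sentence of the Safety section and in its account of sessions one and two.
- Change AR to AE in the minimum data set, and SARs to all SAEs regardless of causality in the annual report. Causality stays as a recorded item.
- State one immediate-reporting rule: which events it covers, and whether any discretion remains with the sponsor.
- Name one responsible recorder, for example the researchers who are already unblinded, and say how therapists' notes reach that log.
- If events are to be reported by arm, ask the same adverse-event question in both arms at the existing post-test and follow-up contacts. Otherwise active questioning in SIESTA sessions alone would make the comparison uneven.

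The cost is a text amendment, one question added to existing contacts if arms are compared, and a few more events to log. No new visits are needed.

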### **Intervention and comparison**

SIESTA is based on a CBT sleep intervention for typically developing adolescents and a CBT intervention focused on motivational planning for adolescents with ADHD, both developed by (amongst others) the project applicants.[36,37] The training follows a structured workbook for the adolescent which can be used during sessions and at home.[24] The instructions for the therapist are described in a therapist manual.[25] SIESTA consists of seven individual sessions with the adolescents, and two parental sessions. An overview of the content of the sessions can be found in Table 2. This RCT uses as control condition TAU for ADHD symptomatology. In Flanders TAU for ADHD primarily consists of medication with stimulants.

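### The only scripted safety question looks back one week and starts at session 3, so it covers the SIESTA course without gaps only from session 2 onward, and only if sessions are never more than 7 days apart

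*Combined protocol and SAP*

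**What the plan says.** The Safety section sets out how events are found during SIESTA:

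- Sessions 1 and 2 have no prompt: "During the first two sessions of the intervention, participants can freely report any adverse event related to the study-specific intervention to their therapist". The stated reason is that these sessions are for building trust.
- After that there is a fixed prompt: "From the third session on the following question will be posed". The question reads "Has anything happened last week that was a danger to you" and gives suicidal thoughts and risk-seeking as examples.
- A general route has no timing: "The participant will be asked to report any adverse event related to the study-specific intervention to the study team".

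Safety considerations, under Ethics and dissemination, summarises this without limiting it to session 3 onward: "Adverse events will be recorded and systematically assessed during the sessions of the treatment".

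On the size of the course, Intervention and comparison says "SIESTA consists of seven individual sessions with the adolescents, and two parental sessions". Table 2 lists one parent session between sessions 3 and 4 and the other between sessions 6 and 7. Neither the interval between sessions nor the course length appears in the text supplied. Ethics & procedure gives the only timing clues. Families are told that "those appointments can either happen as planned or that the treatment will take place 6 months later". The post-test falls no later than a week after the final session, follow-up comes 3 months on, and TAU participants are treated after that.

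**The concern.** A prompt with a fixed one-week window covers the time since the previous session only if that session was at most a week ago. It also cannot reach back to the start of the course when it is first used at session 3.

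Days outside the window depend on the adolescent volunteering the event. Both spontaneous routes in the Safety section are limited to events related to the intervention, and a teenager may not connect suicidal thoughts or binge drinking with sleep training. The scripted question is broader and is the only prompt specified for such events. Ethics & procedure provides for clinicians to be contacted about serious events or a crisis in any phase of the study, but that requires the study to know of the event.

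The population makes irregular spacing foreseeable. The Introduction describes drop-out, non-compliance and severe planning problems, and Table 1 excludes substance abuse but not substance use.

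**Working it through.** **Inputs.** Look-back of 1 week and first prompt at session 3 (Safety). Seven adolescent sessions (Intervention and comparison), so 5 prompts, at sessions 3 to 7, and 6 intervals. This assumes that the question belongs to the adolescent sessions. TAU wait of 6 months, post-test 0 to 1 week after the last session, follow-up at 3 months (Ethics & procedure). A repeat measurement week at follow-up is counted as 0 to 1 week. Conversion: 52.18/12 = 4.348 weeks per month, so 6 months = 26.1 weeks and 3 months = 13.0 weeks.

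**Step 1: can the 6 months be rebuilt?** Elapsed time = course + 13.0 + (0 to 2 weeks of testing).

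- Seven weekly sessions: 6 + 13.0 + (0 to 2) = 19 to 21 weeks, which is 5 to 7 weeks short of 26.1.
- Nine weekly slots, with parent sessions in their own week: 8 + 13.0 + (0 to 2) = 21 to 23 weeks, which is 3 to 5 weeks short.
- Seven fortnightly sessions: 12 + 13.0 + (0 to 2) = 25 to 27 weeks, which matches.

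Fortnightly spacing fits best. Weekly sessions also fit if 3 to 7 weeks go to waiting, holidays or rounding, none of which the text quantifies. The 6-month figure therefore cannot be reproduced without an assumption.

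**Step 2: coverage.** Share covered = total length of the one-week windows before sessions 3 to 7 ÷ time from session 1 to session 7. With sessions a week or more apart the windows do not overlap, so the numerator is 5 weeks. For the rows with a start delay, course = 26.1 − 13.0 − (0 to 2) − delay.

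| Assumption | Course (weeks) | Gap (weeks) | Covered | Not covered |
|---|---|---|---|---|
| Weekly adolescent sessions | 6 | 1 | 5/6 = 83% | 17% |
| Nine weekly slots, order as in Table 2 | 8 | 1, but 2 for sessions 3–4 and 6–7 | 5/8 = 62.5% | 37.5% |
| Fortnightly | 12 | 2 | 5/12 = 42% | 58% |
| Start delay 4 weeks | 7.0–9.0 | 1.2–1.5 | 71–55% | 29–45% |
| Start delay 2 weeks | 9.0–11.0 | 1.5–1.8 | 55–45% | 45–55% |
| No start delay | 11.0–13.0 | 1.8–2.2 | 45–38% | 55–62% |

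**Step 3: the first interval.** With sessions exactly a week apart, the window at session 3 ends at session 2. With wider spacing it stops short of session 2. Either way, no prompt reaches the time between sessions 1 and 2.

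**Step 4: a moved session.** On a weekly calendar, postponing one session (and all later ones) by a week makes the course 7 weeks with 5 covered: 5/7 = 71%, so 29% is not covered.

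**The case against.** A reader might infer that the timeline proves sessions are about two weeks apart and that most of the course escapes the question. The documents do not support that. The text gives no interval or course length. Figure 1, the study procedure, is not shown and could contain the schedule, and the therapist manual is not part of the documents. The 6 months is what families are told, and the Introduction calls the follow-up only approximately three months. Asking about the past week would itself suit weekly sessions.

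A reader might also infer that events on uncovered days have no route to the study. They do: participants are asked to report intervention-related events and may raise them freely in the first two sessions. Table 1 also excludes depressive disorder with suicide risk or active suicidality. These routes lessen the consequence, but they rely on the adolescent volunteering the event and judging it related to the intervention.

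Nor is a planned estimate biased: Statistical analysis contains no adverse-event comparison. This is a matter of finding events, not of inference.

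Finally, a fixed question at every session from the third can fairly be called systematic, and the late start is disclosed and justified. That is right for sessions 3 to 7. It does not describe sessions 1 and 2, and it does not make a one-week window reach the previous session when the gap is longer.

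**Conclusion.** The point holds in a limited form. Continuous coverage by the scripted question cannot be shown from the text. It would require sessions never more than 7 days apart, and even then it would begin only at session 2. With sessions a week or more apart, the first interval is missed whatever the rest of the schedule.

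The uncovered share is about 17% to 62% across the assumptions tried. The low end is strictly weekly sessions with none postponed. The high end is a course filling all the time between the 6-month wait and the 3-month follow-up, with no start delay or testing weeks. Neither end is established, and the range assumes five prompts and full attendance. The conclusion needs no particular value, because the gap arises from a fixed window set against an interval that is unstated in the text and can vary. The change is worth making because it is small and concerns safety ascertainment in minors.

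**What to change.** Change only the time phrase in the scripted question. At sessions 4 to 7 use *since our last session*; at session 3 use *since you started the training*. Keep the session 3 start, with its rapport reason, and the rest of the wording. From session 3 on, each prompt then reaches back to the previous one, and the first reaches back to the start, at any spacing and after any postponement. The session interval need not be settled first.

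Align the sentence in Safety considerations with the Safety section: prompted assessment from session 3, spontaneous reporting before it. On its own this would be only a wording correction.

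The cost is one sentence in the protocol and therapist manual, plus somewhat longer recall. With fortnightly sessions, recall would be 2 weeks at sessions 4 to 7 and 2 × 2 = 4 weeks at session 3, instead of one week.
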